5.4 Curcumin or Placebo

Curcumin or placebo capsules will be given at 4 gm PO twice daily on an empty stomach throughout the chemoradiation therapy period and for six additional weeks. On days of radiation therapy, the capsules will be consumed approximately 1 hour before radiation therapy. On the day that blood is drawn for pharmacology of curcumin or placebo, the 1 hour interval between capsules and radiation may be prolonged (see 7.5). Whenever capecitabine is discontinued, curcumin or placebo will be discontinued as well.

5.5 Patient Monitoring and Supportive Care

Patients will be evaluated weekly by clinicians participating in their care. The clinician will be responsible for performing a history, physical exam, and monitoring lab work. The common acute effects of chemoradiation are managed with aggressive outpatient supportive care. The judicious use of prophylactic antiemetics and a three-step plan to manage diarrhea are used. The goal is to keep the frequency of bowel movements to less than four per day. Patients are initially instructed to take Lomotil as needed. When that is no longer sufficient to control the increased frequency of bowel movement, patients take 2 lomotil every 3-4 hours, which is step 2. Subsequently, Imodium is added and alternated with Lomotil, which is step 3; 2 tablets of one or the other is taken every 2-3 hours. Delayed and immediate release narcotics are used regularly. Another common acute reaction is desquamation of the perineal skin and genitalia, which usually occurs with irradiation of low rectal lesions. These reactions can be effectively managed with lanolin-containing barrier cream used in the perianal area, anusol suppositories for anal canal pain, and Aquaphor for the anterior skin reactions. Moist desquamation often requires narcotic pain medication, sitz baths, and the use of a hydrogel dressing (Vigilon

or Cool Magic).

5.6 Surgery and Adjuvant Therapy

Patients will be evaluated by a surgeon 6-12 weeks after completion of radiotherapy for consideration of surgery. A separate consent form will be obtained for surgery. Further systemic therapy may be offered at the discretion of the treating oncologist.

6.0 Pretreatment evaluation

6.1 Prior to Study Enrollment:

- 6.1.1 Patients must have the following tests before study enrollment:
 - 6.1.1.1 Blood chemistries (bilirubin, alkaline phosphatase, ALT, AST, BUN, creatinine, phosphorus, calcium, glucose, total protein, albumin, and electrolytes [sodium, potassium, carbon dioxide, and chloride], Complete blood count (CBC: hemoglobin, hematocrit, WBC with differential blood cell counts (neutrophils, bands, lymphocytes, monocytes, eosinophils, basophils) and platelets), carcinoembryonic antigen (CEA), urinalysis, all within 10 days of enrollment. PT and INR will be done if patient is on coumadin and phenytoin levels will be checked in patients on phenytoin.
 - 6.1.1.2 Urine pregnancy test within 72 hours of enrollment in women of child-bearing potential
 - 6.1.1.3 Radiographic studies (CXR or chest CT; CT of the abdomen and pelvis) within 30 days of enrollment
 - 6.1.1.4 Colonoscopy within 3 months of enrollment and flexible sigmoidoscopy/ EUS within 30 days of enrollment
 - 6.1.1.5 Endoscopic biopsy prior to study enrollment
- 6.1.2 After consent but prior to initiating chemoradiation therapy, additional tests for research purposes include:
 - 6.1.2.1 MD Anderson symptom inventory (MDASI) questionnaire gastrointestinal module (appendix F)
 - 6.1.2.2 Brief Fatigue Inventory (BFI) (appendix E)
 - 6.1.2.3 Blood collection for cytokine analysis

7.0 Evaluation During Study

During chemoradiation therapy, the patients will be assessed as follows:

- 7.1 Blood chemistries (bilirubin, alkaline phosphatase, ALT, AST, BUN, creatinine, phosphorus, calcium, glucose, total protein, albumin, and electrolytes [sodium, potassium, carbon dioxide, and chloride], and complete blood count (CBC: hemoglobin, hematocrit, WBC with differential blood cell counts (neutrophils, bands, lymphocytes, monocytes, eosinophils, basophils) and platelets) every week. Phenytoin levels will be checked in patients on phenytoin.
- 7.2 Weekly port-films
- 7.3 Weekly MDASI-GI and BFI questionnaires
- 7.4 Weekly blood collection for cytokine analysis
- 7.5 During week 2 (after at least 5 fractions of radiation therapy) of chemoradiation therapy:
 - a) Optional endoscopic biopsy

b) Optional blood collection for pharmacology (1 hour before and 1 hour after intake of curcumin or placebo)

7.6 Patients will be assessed by physician and research nurse at least once every 5 radiation fractions or as needed +/- 1 or 2 radiation fractions

Six-twelve weeks after chemoradiation therapy, patients will be restaged as follows:

7.9 Blood chemistries (bilirubin, alkaline phosphatase, ALT, AST, BUN, creatinine, phosphorus, calcium, glucose, total protein, albumin, and electrolytes [sodium, potassium, carbon dioxide, and chloride], complete blood count (CBC: hemoglobin, hematocrit, WBC with differential blood cell counts (neutrophils, bands, lymphocytes, monocytes, eosinophils, basophils and platelets), and CEA.

7.10 MDASI-GI and BFI questionnaires

7.11 Blood collection for cytokine analysis

7.12 Study Calendar:

Tests & Procedures	Pre-treatment	During chemo-radiation	Week #2 of chemo-radiation	6-12 weeks after chemo-radiation (restaging)	Follow-up (5)
H&P; KPS	x (1)	weekly		x	
CBC (see 6.1)	x (1)	weekly		x	
Serum chemistries (see 6.1)	x (1)	weekly		x	
CEA	x (1)			x	
Phenytoin level (patients on phenytoin)	x (1)	weekly			
PT, INR (patients on coumadin)	x (1)	weekly		x	
Urinalysis	x (1)				
Urine pregnancy test (see 6.1)	x (2)				
Abd-Pelvic CT	x(3)				
Flexible sigmoidoscopy/EUS	x (3)				
Endoscopic ultrasound biopsy	x		x (6)		
CXR	x (3)				
Colonoscopy	x (4)				
MDASI, BFI	x	weekly	x	x	
Cytokines (see 9.2) (6)	x	weekly	x	x	
Pharmacology (see 9.1) (6)			x		
Telephone call (toxicity check)					x

(1) Within 15 days of enrollment
 (2) Urine pregnancy test within 72 hours of enrollment, women of child bearing age only
 (3) Within 30 days of enrollment
 (4) Within 3 months of enrollment

- (5) Telephone call 1 month +/- 1 week after last dose of curcumin/placebo.
- (6) Optional

8.0 Evaluation After Treatment

After finishing chemoradiation treatments and “6 week maintenance (curcumin vs. placebo)”, the patient will have a telephone follow-up visit 1 month +/- 1 week. Since most surgeries take place within the 1-3 weeks after the 6 week maintenance, the patient will typically be in surgical planning/ implementation/recovery. Furthermore, since most patients are from out of town, this follow-up visit is best accomplished via a telephone call. Therefore, toxicity check will be verbal and a note will be recorded in the patient’s chart. Surgical toxicity will not be recorded since it is likely that patients will complain of incisional discomfort, abdominal pain, and symptoms related to surgery. Most side effects of chemoradiation would have resolved by the time of this telephone call.

Patients may receive adjuvant chemotherapy after surgery, at the discretion of the treating medical oncologist.

Standard-of-care follow-up evaluations will be undertaken per the directions of the treating medical oncologist. The patient chart will be reviewed periodically to capture failure and survival information.

9.0 Correlative Studies

9.1 Clinical pharmacology studies (optional)

9.1.1 Blood samples (20 ml) will be collected in lavender top tubes at the Endoscopy suite during the second week of CRT and processed as follows. This will be performed pre-dose and 1-hour +/- 10 minutes post-dose of curcumin or placebo. A third of the sample will be centrifuged immediately (1500 x g for 15 min at 4°C). The plasma is removed and stored at -20°C. The samples will be shipped in the frozen state for storage until ready for analysis in the core pharmacology lab. The remaining two-thirds of the sample will be transferred into a 50 cc conical tube to which is added an equal volume of PBS. The tube is inverted 10 times. The diluted blood is transferred to another 50 ml conical tube that contains an equal volume of Ficoll-Paque using a transfer pipette. The diluted blood is carefully laid over the Ficoll-Paque at room temperature. The tube is capped and centrifuged (700 x g for 30 min) at room temperature using a swinging bucket rotor. Cells (peripheral blood mononuclear cells, PBMC) are obtained at the resulting interface, transferred to another tube and washed once with PBS. After centrifugation, cells are then resuspended, and samples saved for immunocytochemical analyses.

9.1.1.1 Plasma curcumin, curcumin glucuronide, curcumin sulfate, demethoxycurcumin, and bisdemethoxycurcumin will be measured using high-performance liquid chromatography and mass spectrometry.

- 9.1.1.2 Curcumin and its metabolites will be expressed in micrograms of drug per milliliter of plasma.
- 9.1.1.3 Results will be expressed as means +/- standard deviations.
- 9.1.1.4 PBMC will be used for immunocytochemical analysis.
- 9.1.2 Biopsies (tumor) will be obtained during the second week of chemoradiation therapy and at restaging. Surgical specimen will also be collected.
 - 9.1.2.1 Biopsy tissue and surgical tissue will be immediately frozen in liquid nitrogen and stored at -80°C. The tissue will be homogenized (liquid nitrogen cooled mortar and pestle, cold spatula transfer to cooled eppendorf, cryocentrifuged, digested, homogenized in ultrasonic homogenizer) and then analyzed for targets (curcumin and its metabolites) as noted above.
 - 9.1.2.2 Curcumin and its metabolites will be expressed in micrograms of drug per milligram of wet tissue weight.
 - 9.1.1.3 Results will be expressed as means +/- standard deviations.

9.2 Cytokine assays (optional)

These will be performed by personnel who are blinded to the treatment status of the patients.

- 9.2.1 Blood will be collected in lavender top tubes at study initiation and weekly during chemoradiation for cytokine analyses. This will be stored in the laboratory until bunched samples can be analyzed in the core cytokine lab. The cytokines assayed will include IL-1b, IL-8 and TNF-a.

9.3 Surrogate marker analyses

These will be performed by personnel who are blinded to the treatment status of the patients.

Fresh frozen tumor from biopsy and surgical specimens will be processed for correlative studies as noted below:

- 9.3.1 A portion of tumor tissue will be snap frozen for measurement of drug levels as noted in 9.1.2.
- 9.3.2 A portion will be frozen for Western blot analysis, electrophoretic mobility shift assay, and microarray analysis. Tissue will be homogenized and probed with specific antibodies for Western blot analysis of key proteins including bcl-2, bax, PARP, VEGF, cyclin D1, and cox-2. Nuclear extracts will be prepared for EMSA of NF- κ B DNA-binding.
- 9.3.3 Another portion will be processed for immunohistochemical analysis including p65, p-stat3, cox-2, VEGF, Ki-67, and CD31 evaluation.
- 9.3.4 The remainder will be frozen for further analysis.
- 9.3.5 Labeled sterile Nunc tubes will be used to store tissue samples.
- 9.3.6 All tissue not mentioned above will be routinely processed as per the pathology department.

10.0 Criteria for Toxicity

Patients will be evaluated each week during chemoradiation just before surgery and 1 month +/-

2 days after surgery by a physician and research nurse regarding the occurrence and nature of any adverse events. Appendix B provides the grades to be assigned for various types of toxicities.

10.1 Off-study criteria

Patients who have documented clinical progression of disease that is discovered upon symptomatic progression during therapy will be taken off study. Patients will be taken off study if they fail to complete protocol therapy for reasons other than treatment related toxicity or tumor progression and will not be counted in the analysis. Patients will be taken off study if they miss two consecutive appointments.

10.2 Criteria for Discontinuing Therapy

Treatment will be discontinued if an unpredictable, irreversible toxicity develops, or patient chooses to discontinue treatment/study.

10.3 See 12.0 for reporting requirements.

11.0 Data and Protocol Management

11.1 Patients will be registered by calling a Radiation Oncology Research Nurse, who will then register them on the MDACC computerized Clinical Oncology Research System (CORe).

12.0 Reporting Guidelines

- 12.1 All serious adverse events described in Appendix A will be reported to the IRB. Serious adverse events will be delivered to the Office of Research Education and Regulatory Management - IND office and will be submitted to the FDA by the Project Manager for IND safety, according to 21 CFR 312.32.
- 12.2 Surgical complications will not be reported.
- 12.3 Lymphopenia, high blood sugar and electrolyte abnormalities will not be reported.
- 12.4 Toxicities grade 2 and above will be captured in PDMS data.

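### Section 10.0 requires an adverse-event assessment one month after surgery that the study calendar omits, and sections 8.0 and 12.2 leave no clear rule for serious postoperative events

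*Combined protocol and SAP*

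**What the plan says.** Section 10.0 (Criteria for Toxicity) has patients evaluated weekly during chemoradiation, just before surgery, and again at one month plus or minus "2 days after surgery by a physician and research nurse regarding the occurrence and nature of any adverse events". Section 10.3 then points onward: "See 12.0 for reporting requirements".

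The study calendar (7.12) has columns for pre-treatment, chemoradiation, week 2, restaging at 6-12 weeks, and follow-up. No column is tied to surgery. The only follow-up entry is a toxicity check by telephone, defined in footnote 5: "Telephone call 1 month +/- 1 week after last dose of curcumin/placebo".

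Section 8.0 describes the same call. "Therefore, toxicity check will be verbal and a note will be recorded" in the chart, and the next sentence reads: "Surgical toxicity will not be recorded since it is likely that patients will complain of incisional discomfort, abdominal pain, and symptoms related to surgery". It gives the usual timing of surgery ("Since most surgeries take place within the 1-3 weeks after the 6 week maintenance") and one further source of data: "The patient chart will be reviewed periodically to capture failure and survival information".

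Section 12.1 sends the serious adverse events described in Appendix A to the IRB. It sends serious adverse events to the IND office and on to the FDA under 21 CFR 312.32. Section 12.2 says "Surgical complications will not be reported". Section 12.3 exempts lymphopenia, high blood sugar and electrolyte abnormalities. Section 12.4 has toxicities of grade 2 and above captured in PDMS and mentions no surgical exception.

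**The concern.** Section 10.0 and the calendar give different answers to a simple question: is a patient assessed for adverse events after the operation? Section 10.0 says yes, by two named roles, within a tight window and for any event. A site working from the calendar would find only a telephone call, timed from the last capsule, at which surgical toxicity is not noted.

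The reason offered in 8.0 is that incisional discomfort, abdominal pain and similar complaints are expected. That justifies leaving out expected symptoms. It does not explain leaving out serious complications, yet neither 8.0 nor 12.2 draws that line.

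At stake is the safety description in a trial where surgery is part of the design: pCR is read at surgery, and most operations follow the capsules within weeks. The chart review in 8.0 would still find deaths, but it is described as covering failure and survival only. Non-fatal serious complications have no assured route into the data when curcumin is considered for further development.

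**Working it through.** **Passages side by side**

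| Item | Section 10.0 | Section 8.0 and calendar footnote 5 |
|---|---|---|
| Timed from | surgery | last capsule |
| Window | one month ± 2 days | one month ± 1 week |
| Mode | physician and research nurse | verbal, by telephone |
| Scope | any adverse event | toxicity check, surgical toxicity not recorded |

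All four rows differ. Sections 8.0 and 7.12 agree with each other on timing, so the conflict is between 10.0 and that pair.

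**Could one contact serve both?** Let day 0 be the last capsule, s the day of surgery and M one month in days. Section 8.0 gives s = 7 to 21 for most patients.

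- Call window: M − 7 to M + 7.
- 10.0 window: s + M − 2 to s + M + 2.
- Overlap requires s + M − 2 ≤ M + 7, so s ≤ 9. M cancels, so a month of 28, 30 or 31 days gives the same limit.

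With M = 30 the call falls on days 23-37:

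| Surgery on day | 10.0 window (days after last capsule) | Overlap with call |
|---|---|---|
| 7 | 35-39 | 35-37 |
| 9 | 37-41 | 37 only |
| 10 | 38-42 | none |
| 21 | 49-53 | none |

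Days 7 to 21 are 15 possible surgery days. Overlap exists on three of them (7, 8 and 9), and only if the call is made 5 to 7 days late. This counts calendar days, not patients.

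**What the call sees after surgery (M = 30).** It falls 23 − 21 = 2 to 37 − 7 = 30 days after the operation. Made exactly on schedule, it falls 30 − 21 = 9 to 30 − 7 = 23 days after. Section 10.0 asks for days 28-32.

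**Later or earlier end of capsules.** Section 5.6 has the surgeon evaluate patients 6-12 weeks after radiotherapy. With the full six weeks of maintenance (5.4), that is 0 to 42 days after the last capsule, so some operations can come after the latest call (day 37). Section 5.4 also stops the capsules when capecitabine is discontinued. If that happens on or before the last radiation day, the latest call (day 37, or 38 with a 31-day month) comes before the earliest surgeon evaluation (day 42 or later), and the call cannot see any postoperative event. The documents do not say how often either case arises.

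**Reporting of a serious surgical complication.** Two readings fit the text.

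- Narrow: the 8.0 exclusion applies only to the telephone note, and 12.2 limits onward reporting but not capture. Surgical events of grade 2 and above are then captured through 10.0 and 12.4, provided staff hold an assessment that the calendar does not list.
- Broad: both clauses cover all surgical events, and non-fatal serious complications are neither recorded nor reported.

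On either reading, sections 12.1 and 12.2 do not state which prevails when a surgical complication is serious.

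**The case against.** The best defence has several parts. Section 10.0 does schedule the post-surgery assessment, and its absence from a summary calendar does not cancel it. The telephone call is a study-treatment toxicity check, sensibly timed from the last capsule, and two contacts with different purposes need not overlap. Sections 12.2 and 12.3 follow the general rule in 12.1 as consecutive items not to be reported, and read naturally as exceptions to it. Appendix A, on which 12.1 relies, was not in the text available here and may settle the matter. Surgery has its own consent form (5.6), and toxicity is not among the objectives in 1.0.

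Much of this stands. A reader might infer that sections 8.0, 10.0, 12.1, 12.2, 12.4 and the calendar all contradict one another. They do not: 8.0 agrees with the calendar on timing and with 12.2 on leaving surgical events out, and a chart note under 8.0 can coexist with PDMS capture under 12.4. Nor is 12.1 against 12.2 a proven contradiction; it is an unstated precedence. A reader might also take three of 15 days as a share of patients, but no distribution of surgery dates is given.

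What the defence does not answer is that 10.0 covers any adverse event after surgery while 8.0 leaves surgical toxicity out, and that the calendar gives staff no prompt for the 10.0 assessment. Reading 12.2 as a deliberate exception would also leave its breadth unexplained, since the reason in 8.0 reaches only expected symptoms.

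**Conclusion.** The mismatch between 10.0 and the pair formed by 8.0 and the calendar is real and should be corrected. The call cannot replace the 10.0 assessment when surgery falls after day 9 following the last capsule, which covers days 10 to 21 of the usual interval. That result does not depend on the length of a month; it does take the 1-3 weeks in 8.0 as days 7 to 21.

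The scope of 12.2 for serious complications is unclear rather than shown to be wrong, and it remains subject to Appendix A. It would go too far to conclude that serious complications will certainly be lost: under the narrow reading they are captured if staff carry out 10.0.

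The possible loss is to the description of safety. The documents give no surgical complication rate, so no event count is offered. No passage links curcumin to surgical morbidity, and no effect on the primary analysis is claimed.

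**What to change.** Reconcile the passages in one amendment:

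1. Either list the 10.0 post-surgery assessment in the study calendar, or amend 10.0 so that chart abstraction over the month after surgery replaces it.
2. Limit the non-recording clause in 8.0 to the expected symptoms it names.
3. State in 12.2 whether serious postoperative events follow 12.1, and in 12.4 whether surgical events of grade 2 and above are captured.
4. Record serious postoperative complications from the charts already reviewed under 8.0, so that they can be described by arm. No hypothesis test is needed.

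The cost is a short amendment, a few more chart items and some added paperwork for serious adverse events. If chart abstraction is chosen, no visit or procedure is added. A fuller toxicity table in 13.0 is a separate question and is not needed to resolve this one.

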13.0 Statistical Considerations

The Department of Biostatistics will create a randomization website to be used by the pharmacists to assign treatments to patients. Patients will be randomized to control and experimental treatment arms in a 1:2 ratio. That is, the probability of a patient being randomized to the control arm (placebo) is 1/3, while the probability of a patient being randomized to the experimental arm (curcumin) is 2/3. The primary outcome for this trial is the pCR rate, which is evaluated at the time of surgery. We expect the pCR rate to be 18% in the control group (3, 5, 15).

Our target pCR rate is 36% or more in the curcumin treatment group. For those patients randomized to curcumin we will employ a two-stage design with a significance level of 10% and 80% power. We will treat 16 patients in the first stage, and if there are 3 or more patients with pCR among these first 16 patients, we will treat 14 additional patients in the second stage, for a total of 30 patients. Curcumin will be considered for further development if there are 9 or more patients with pCR among these 30 patients. The probability of stopping the study after the first stage if the pCR rate is 18% is 0.43, while the probability of stopping the study after the first

stage if the pCR rate is 36% is 0.04. The expected sample size for this two-stage design is 24 patients, and the actual significance level is 7.5%." and replace it with "The expected sample size if the pCR rate is 18% is 24, and the actual significance level is 7.5%. We will randomize 15 patients to the placebo arm, yielding a total maximum sample size of 45 patients. We will accrue patients at a rate of 4 patients per month.

Secondary Outcomes

Downstaging

We will also compare the 2 treatment arms with respect to the proportions of patients that are downstaged at the time of surgery. We expect the proportion of patients in the control arm that will be downstaged is 60% (3, 5, 15). With 15 patients in the control arm and 30 patients in the experimental arm, we will have 82% power to detect an increase in the proportion of patients that are downstaged to 95%.

Correlative Studies

For the experimental treatment we will compare the concentration of curcumin in the tumor with the curcumin concentration levels in serum. We will find the difference in curcumin concentration levels in tumor and serum for each patient (tumor – serum), and then we will use a paired t-test to determine whether the mean difference is statistically significant.

For the experimental treatment we will estimate the correlation between the curcumin level in tumor tissue and 1) NF- κ B activity, and 2) pCR. We will also estimate the correlation between the curcumin level in serum and these same variables.

We will use a logistic regression model with pCR as the dependent variable to assess the association between pCR and NF- κ B activity and treatment.

We will also compare between treatment groups changes in selected components of known relevant pathways in both normal and tumor tissue. These include bcl-2, bax, PARP, VEGF, cyclin D1, p-stat3, Ki-67, CD31 and cox-2.

Quality of Life and Toxicity

Patients will complete validated quality of life (QoL) instruments at baseline and weekly during chemoradiation. These instruments include the MD Anderson Symptom Inventory-Gastrointestinal (MDASI-GI) and Brief Fatigue Inventory (BFI). A panel of cytokines (IL-1 β , IL-8 and TNF- α) will be assayed at these same evaluation times. We will estimate the correlation between the various cytokine levels and the various QoL instrument scores.

We will also compare changes from baseline in cytokine levels between treatment groups using a repeated measures analysis of variance model. We will construct side-by-side boxplots of changes from baseline in cytokine levels by treatment group for each evaluation time. We will also construct side-by-side boxplots of changes from baseline of QoL instrument scores by treatment group for each evaluation time.

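### Is the tumour-minus-serum curcumin comparison invalid because tissue and plasma are reported in different units?

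*Combined protocol and SAP*

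**What the plan says.** Section 13.0 (Correlative Studies) sets out the comparison for the curcumin arm: "We will find the difference in curcumin concentration levels in tumor and serum for each patient", tumour minus serum, and "then we will use a paired t-test to determine whether the mean difference is statistically significant". It gives no unit, test level, power or expected difference. The same part of the section plans correlations of the tumour level with NF-κB activity and pCR, and adds: "We will also estimate the correlation between the curcumin level in serum and these same variables".

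Section 9.1 fixes how each matrix is reported. For blood (9.1.1.2): "Curcumin and its metabolites will be expressed in micrograms of drug per milliliter of plasma". For tissue (9.1.2.2): "Curcumin and its metabolites will be expressed in micrograms of drug per milligram of wet tissue weight". Each is then to be summarised by its mean and standard deviation.

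On blood timing, section 9.1.1 collects the pharmacology sample in the second week of chemoradiation and says: "This will be performed pre-dose and 1-hour +/- 10 minutes post-dose of curcumin or placebo". On tissue timing, section 9.1.2 says: "Biopsies (tumor) will be obtained during the second week of chemoradiation therapy and at restaging", and adds the surgical specimen. Section 8.0 places surgery later: "Since most surgeries take place within the 1-3 weeks after the 6 week maintenance".

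**The concern.** Subtraction needs both terms in one unit, and section 9.1 specifies two. An analyst who paired the two reported columns and ran the t-test would get a number with no physical meaning. Because a tissue value in micrograms/mg looks about 1000 times smaller than the same concentration in micrograms/mL, the result could show blood above tumour when tumour is in fact higher.

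That direction is of interest. Objective 1.2.2 is to describe serum and tumour pharmacology, and section 3.3.5 cites earlier work with relatively high colorectal tissue levels and only trace levels in the circulation. The tumour-serum difference is the only planned test of that pattern.

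Three smaller gaps lie in the same sentences. Section 13.0 does not say which of the two blood draws is used, does not say which tissue sample is used, and says serum where section 9.1.1.1 assays plasma.

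**Working it through.** The plan gives no sample size or expected difference for this comparison, so there is no figure of its own to reproduce. The check covers the units, the sampling schedule and the correlations.

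**Inputs.** Molecular weight 368.37 (section 3.3.1). Malignant tissue level 7.7 nmol/g at 3.6 g daily (section 3.3.5). Planned dose 4 g twice daily, which is 8 g daily (section 5.4). Tissue density 1.0 to 1.1 g/mL (assumed). The documents give no plasma concentration, so plasma is varied over an assumed range.

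**Scale factor.** 1 microgram/mg = 1000 micrograms/g = 1000 × density micrograms/mL, which is 1000 to 1100 over the assumed densities.

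**Tissue level in both units.** 7.7 nmol/g × 368.37 ng/nmol = 2836 ng/g = 2.84 micrograms/g. In the unit of 9.1.2.2 this is 0.00284 micrograms/mg.

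**Difference as reported and after conversion, at 1 g/mL.**

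| Assumed plasma (micrograms/mL) | Unconverted: 0.00284 − plasma | Common unit: 2.836 − plasma |
|---|---|---|
| 0.001 | +0.0018 | +2.835 |
| 0.01 | −0.0072 | +2.826 |
| 0.1 | −0.097 | +2.736 |
| 1 | −0.997 | +1.836 |

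The signs disagree when mean plasma lies between 0.00284 and 2.84 micrograms/mL. If tissue level rose in proportion to dose (assumed), 7.7 × 8/3.6 = 17.11 nmol/g = 6.30 micrograms/g, and the window would be 0.0063 to 6.30. Below the lower limit even the unconverted difference has the right sign.

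**How much the density assumption matters.** At 1.1 g/mL the cited tissue level is 2.836 × 1.1 = 3.12 micrograms/mL instead of 2.84, a 10% change. That could affect the sign only if plasma were almost equal to tissue.

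**Which samples form the pair.**

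- Section 7.5 lists the optional biopsy and the optional pharmacology blood together under week 2.
- The calendar in 7.12 puts both in the week 2 column. It shows no biopsy and no pharmacology sample at restaging.
- Section 9.1.1 has the blood drawn in the endoscopy suite.
- Surgical tissue comes much later. With 28 fractions at five a week and no breaks, chemoradiation lasts 28/5 = 5.6 weeks. Six weeks of maintenance and 1 to 3 weeks to surgery bring the total to 12.6 to 14.6 weeks, or 10.6 to 12.6 weeks after the end of week 2.

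Week 2 is therefore the only time at which the schedule provides both matrices.

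**Correlations.** Multiplying one variable by a positive constant leaves a correlation unchanged. The planned correlations with NF-κB activity and pCR are the same in either unit.

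**The case for a change.** The strongest case for a change is that a prespecified test should be computable from the plan as written. Section 9.1 is explicit about the two units, and no section gives a common unit, a density, or a ratio or log-scale alternative. The cost would be a sentence or two, with no new samples or assays.

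The facts in that argument stand: both units are as described, no conversion is given, and the factor is about 1000. The harm does not follow from them. Section 9.1 says how each matrix is reported for its own summary. Section 13.0 separately calls for a difference in concentration, which only makes sense in one unit. An error would need someone to subtract columns labelled per mg and per mL without noticing, and then to accept a result contrary to the tissue-versus-blood pattern that section 3.3.5 describes. The density assumption is ordinary and, as shown, seldom material.

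The choice of tissue sample is largely settled by the schedule. Section 9.1.2 does also list restaging and surgical tissue, so section 13.0 could have named the week 2 biopsy. The choice between the pre-dose and the one-hour draw is truly open, and unlike the units it bears on the correlations of blood level with pCR and NF-κB activity. Those are descriptive estimates with no decision attached, and both draws can be reported. The word serum is loose, but anyone following section 9.1 would assay plasma.

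**Conclusion.** The unit mismatch is real on paper, but it is missing detail of the kind an analyst supplies as a matter of course. The paired t-test, the samples and the assays are all usable as planned once both matrices are in one unit, for example micrograms/g for tissue and micrograms/mL for plasma with 1 g taken as about 1 mL.

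The sign window of 0.0028 to 2.84 micrograms/mL shows what would happen if nobody converted. It does not show that this is likely. It rests on a tissue level from a different dose and setting, and on an assumed density. With no plasma concentration in the documents, no probability of error can be given. Working out where an unconverted test would lose significance would also need an assumed plasma spread, number of pairs and test level, so no such figure is offered.

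The reach is small. Sampling is optional, at most 30 curcumin patients can contribute, and the comparison feeds no stopping rule, pCR decision or sample size. The blood draw and the wording on serum are points to tidy when the analysis is written up. No change to the plan is called for.
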